Following SBRT, all patients will restart MK-3475 as soon as feasible. They will continue until they have further progression of disease, defined as irPD, or at the discretion of the treating physician if they are felt to receiving clinical benefit.

If MK-3475 is held at any point during a subject's participation in the trial for any reason, the subject will be followed as per standard of care until treatment with MK-3475 is resumed. When treatment with MK-3475 is resumed, the subject will continue with Day 1 procedures for the next planned cycle.

The **phase 2a portion** is an expansion cohort with enrollment closing when 20 NSCLC patients have been enrolled (including those enrolled on phase I). Similar to the phase Ib portion, NSCLC patients who initiated trial therapy on MK-3475 will receive MK-3475 until there is progression of disease (irPD). Patients who do not have progression of disease within that timeframe may continue to receive MK-3475 for up to 18 months per protocol. These patients will not be evaluable for the study endpoints, although their response rates and overall survival will be reported. NSCLC patients will be enrolled after they have irPD on anti-PD-1 therapy received prior to study entry. After progression, an SBRT target will be selected and patients will be treated at the SBRT MTD as determined in the Phase Ib portion of the study, for lung and non-lung targets. The SBRT target will be chosen and ideally SBRT will be delivered as quickly as feasible after the last infusion of MK-3475. In the event of drug-related toxicity or other delay, SBRT may start up to 12 weeks after the last infusion as detailed below in section 5.2.3. Following SBRT, all patients will receive MK-3475 until they develop progression of disease (as defined by irPD), or until they are no longer receiving clinical benefit.

For each phase of the study, the first course of MK-3475 will start on day 1, and will be given every 3 weeks (+/- 7 days) (one cycle). Patients will undergo re-imaging CT of the chest, abdomen, and pelvis at the end of cycle 2, cycle 4, and every 4 cycles thereafter (i.e., at cycles 8, 12, etc.). After the SBRT, when MK-3475 is re-initiated, imaging will be done at the end of cycles 2, 4, and then every 4 cycles. Exceptions to the timing of re-imaging can be made by the treating investigator as necessary to determine course of treatment.

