5.7 Subject Withdrawal/Discontinuation Criteria

Subjects may withdraw consent at any time for any reason or be dropped from the trial at the discretion of the investigator should any untoward effect occur. In addition, a subject may be withdrawn by the investigator if enrollment into the trial is inappropriate, the trial plan is violated, or for administrative and/or other safety reasons. Specific details regarding discontinuation or withdrawal are provided in Section 7.

A subject must be discontinued from treatment, or removed from the study for any of the following reasons:

- The subject or legal representative (such as a parent or legal guardian) withdraws consent.
- Progression of disease during the second course of MK-3475 (as defined in section 5.2.1)
- Unacceptable adverse experiences as described in Section 5.2
- Intercurrent illness that prevents further administration of treatment
- Investigator's decision to withdraw the subject
- The subject has a confirmed positive serum pregnancy test

- Noncompliance with trial treatment or procedure requirements
- The subject is lost to follow-up
- Completed 12 months of treatment with post-SBRT MK-3475
Note: 12 months of study medication is calculated from the date of first dose of the second course. Subjects who stop MK-3475 after 12 months will be eligible for up to one year of additional study treatment if they progress after stopping study treatment
- Administrative reasons

The End of Treatment and Follow-up visit procedures are listed in Sections 6 and 7. After the end of treatment, each subject will be followed for 30 days for adverse event monitoring (serious adverse events will be collected for 90 days after the end of treatment as described in Section 8). Subjects who discontinue treatment will be followed for survival until death, withdrawal of consent, or the end of the study, whichever occurs first. Survival follow up may be a phone call only.

58 Subject Replacement Strategy

In both phases of the study, patients will be replaced if

1. They do not complete at least one fraction of SBRT.
2. They do not complete their entire course of SBRT as prescribed due to reasons other than toxicity (e.g., patient refusal, or intercurrent illness).

59 Clinical Criteria for Early Trial Termination

Early trial termination will be the result of the criteria specified below:

1. Quality or quantity of data recording is inaccurate or incomplete
2. Poor adherence to protocol and regulatory requirements

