9.0 STATISTICAL ANALYSIS PLAN

In the phase 1b portion of the trial, patients will be enrolled in parallel dose escalation cohorts using the “Rolling Six” method, as described in Section 5.

The primary endpoint of the phase 2a portion of the study is the response rate to post-SBRT MK-3475, separately determined for a NSCLC cohort. A total of 12 patients will be treated at the MTD in the first phase of the study (6 each of lung and non-lung SBRT

targets), and we project that this will include an approximately equal number of NSCLC and melanoma patients. In the second phase of the study, an expansion cohort will be enrolled until a total of 20 NSCLC patients eligible to undergo SBRT is reached (including NSCLC patients treated in the phase I and II portions of the study). We project that approximately 30% of patients (unselected for PD-L1 expression) will respond to the initial MK-3475 for 12 months or more and be replaced. Of those who go on to progress and be SBRT, we estimate that 30% will drop out, or otherwise be ineligible for assessment of response to post-SBRT MK-3475.

There is no published data to suggest a historical control for response to re-treatment with MK-3475, in patients who have been previously treated with MK-3475 and have prior documented progression of disease. In melanoma patients treated with anti-CTLA4 antibody, there is a documented response rate for re-treatment of patients who previously responded and subsequently progressed. In a series of 31 patients who initially had a partial or complete response, and then had progression of disease, re-induction with antibody resulted in a response in 13% of patients. It should be noted, however, that treatment beyond standard RECIST criteria was not permitted in the initial treatment course for these patients, so some may have had pseudoprogression. It is therefore presumed that the expected ORR without SBRT in this population, allowing for treatment beyond RECIST in their initial therapy with MK-3475 is less than 5%. If 4 of 20 patients (20%) in the NSCLC expansion cohort develop a partial or complete response to post-SBRT MK-3475, this strategy will be deemed worth of further investigation. The 95% confidence interval will be (0.05, 0.49) by using one-sample proportion test with continuity correction.

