The primary endpoint of this trial will be response rate and the secondary endpoint will be progression-free survival. We will use descriptive statistics to calculate frequency and proportion for the response rate to post-SBRT MK-3475. 95% confidence interval will also be provided. Exact binomial test will be used to compare the observed response rate versus historical control. For the secondary endpoint, we will use Kaplan-Meier estimator to present the progression-free survival.

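### The 95% CI printed beside the 4-of-20 success rule is not the interval for 4/20, and the rule does not say how treated patients without a response assessment are counted

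*Combined protocol and SAP*

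**What the plan says.** All of the following is in the combined protocol and SAP.

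- **Success rule, Section 9.0.** The strategy merits further study on this condition: "If 4 of 20 patients (20%) in the NSCLC expansion cohort develop a partial or complete response to post-SBRT MK-3475". The response rate without SBRT is presumed to be below 5%.
- **Interval, Section 9.0.** The next sentence reads: "The 95% confidence interval will be (0.05, 0.49) by using one-sample proportion test with continuity correction".
- **Test, Section 9.0.** "Exact binomial test will be used to compare the observed response rate versus historical control". No alpha, sidedness or alternative response rate is given.
- **Expected losses, Section 9.0.** About 30% of patients "will respond to the initial MK-3475 for 12 months or more and be replaced". Of those who go on to SBRT, "we estimate that 30% will drop out, or otherwise be ineligible for assessment of response to post-SBRT MK-3475".
- **Cohort size.** Section 9.0 recruits "until a total of 20 NSCLC patients eligible to undergo SBRT is reached". Section 5.2.1 describes an "expansion cohort with enrollment closing when 20 NSCLC patients have been enrolled (including those enrolled on phase I".
- **Replacement.** Section 5.8 replaces patients on one of two grounds. The first is "They do not complete at least one fraction of SBRT"; the second is a course of SBRT left unfinished for reasons other than toxicity. Section 5.2.3 and footnote 7 of the first study calendar add replacement for certain failures before SBRT: listed events that do not resolve in time, or no target selected in time.
- **Evaluability.** Section 5.2.1 calls patients not evaluable only when they do not progress on the initial MK-3475. Sections 9.0, 12.0 and 12.1 define no analysis population for the response rate and no rule for a missing response.

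**The concern.** The 4-of-20 rule is the only efficacy criterion that the plan states. A reader who checks the interval beside it with the method named there does not get the printed figures, so the plan misstates the precision it would have at its own decision boundary.

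The second issue is what the 20 means for patients who were treated but never assessed. The plan itself expects a sizeable share of such losses. The rule is given both as a count (4 of 20) and as a percentage (20%), and the two can part company once patients are removed from the denominator. Patients lost before a first scan are unlikely to have been responders, so removing them would tend to raise the response rate. If the choice is not written down, it could be made after the responses are known in an open-label, single-arm trial.

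**Working it through.** **Inputs.** x = 4, n = 20, the 95% level, the continuity-corrected one-sample method, the presumed rate of 5% and the expected 30% loss all come from Section 9.0.

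**1. The plan's own figure.** The interval that goes with the continuity-corrected one-sample proportion test is the corrected score interval. With p = x/n and z² = 3.8415:

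- lower = [2np + z² − 1 − z√(z² − 2 − 1/n + 4p(n(1 − p) + 1))] / [2(n + z²)]
- upper = [2np + z² + 1 + z√(z² + 2 − 1/n + 4p(n(1 − p) − 1))] / [2(n + z²)]

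For 4/20, 2np = 8 and the divisor is 2 × 23.8415 = 47.683.

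- lower = (8 + 3.8415 − 1 − 7.689) / 47.683 = 0.066
- upper = (8 + 3.8415 + 1 + 8.267) / 47.683 = 0.443

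The printed (0.05, 0.49) is not reproduced. Other 95% intervals for 4/20 do not give it either:

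| Method | Lower | Upper |
|---|---|---|
| Clopper-Pearson | 0.057 | 0.437 |
| Score, uncorrected | 0.081 | 0.416 |
| Wald | 0.025 | 0.375 |
| Agresti-Coull | 0.075 | 0.422 |
| Jeffreys | 0.072 | 0.408 |

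Changing the confidence level of the corrected score interval does not help: 90% gives (0.077, 0.406), 98% gives (0.056, 0.485) and 99% gives (0.050, 0.513).

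**2. What the printed pair does fit.** Among all x/n with n from 5 to 60, the stated method rounds to (0.05, 0.49) only for 3/15, which is also 20%. There 2np = 6 and the divisor is 2 × 18.8415 = 37.683.

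- lower = (6 + 3.8415 − 1 − 6.839) / 37.683 = 0.053
- upper = (6 + 3.8415 + 1 + 7.483) / 37.683 = 0.486

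**3. The rule read as a count.** At a true rate of 5%, the probabilities of 0, 1, 2 and 3 responders among 20 are 0.3585, 0.3774, 0.1887 and 0.0596. So P(X ≥ 4) = 1 − 0.9842 = 0.016.

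**4. Who is left uncovered.** Setting the provisions side by side:

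| Patient | Provision |
|---|---|
| No progression on initial MK-3475 | Not evaluable (5.2.1) |
| Listed event unresolved, or no target selected in time | Replaced (5.2.3; calendar footnote 7) |
| No SBRT fraction completed | Replaced (5.8) |
| SBRT unfinished, not for toxicity | Replaced (5.8) |
| SBRT completed, then no response assessment | None |
| SBRT stopped for toxicity, then no response assessment | None |

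**5. What dropping the last two groups could do.** If all of the 30% fell there, 20 × 0.7 = 14 patients would be assessable. One-sided exact p for 3 responders against 5%:

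| Denominator | Rate | p | Reaches 20%? |
|---|---|---|---|
| 14 | 21% | 0.030 | yes |
| 15 | 20% | 0.036 | yes |
| 16 | 19% | 0.043 | no |
| 20 | 15% | 0.075 | no |

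Three responders can therefore pass on the percentage only if at least 5 of the 20 are dropped.

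**6. Chance of success with 14 of 20 assessable.** The plan states no alternative rate, so 20% and 30% are assumptions.

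| Rule | True ORR 20% | True ORR 30% |
|---|---|---|
| 4 or more responders, all 20 in the denominator | 0.30 | 0.64 |
| At least 20% of the 14 assessable (3 or more) | 0.55 | 0.84 |

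**The case against.** The strongest reply is that neither point affects the decision. The interval is a planning figure, and Section 9.0 promises a 95% interval with the observed result, which will supersede it. The printed interval is wider than the right one. The rule prints both its count and its denominator, with the 20% only in brackets, so the plain reading is 4 responders among 20. For 3 responders to pass, three things must happen together: patients are dropped, the percentage replaces the count, and at least 5 of 20 are unassessable. Even then the type I error at 5% is 0.030 with 14 assessable and 0.036 with 15, and the plan states no alpha for this to breach. The sentence on 30% loss follows an accrual projection and may itself be about recruitment.

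Most of this stands, and it limits the point. It does not make the printed interval right, and it does not supply a rule for the uncovered patients.

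Three stronger readings are tempting, and the documents do not support them:

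- **A reader might infer that the cohort was really sized at 15.** The match with 3/15 is suggestive, but no section mentions 15 patients.
- **A reader might infer that the plan will analyse 14 patients.** That is a worst case. Section 5.8 may replace some of the 30%, and the documents do not say how many would remain uncovered.
- **A reader might infer that Sections 5.2.1 and 9.0 set two different sample sizes.** The replacement provisions bring the two counts close together. The difference is mainly one of wording, although Section 5.2.1 does not say that replaced patients are left out of its count.

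**Conclusion.** The printed interval is wrong as it stands. For 4/20 it should be (0.07, 0.44) by the stated method or (0.06, 0.44) exact; the printed upper limit is about 0.05 too high and the lower about 0.01 to 0.02 too low. This rests only on the stated method and on 4/20. It changes no decision, because the corrected lower limits (0.066 and 0.057) remain above the presumed 5%.

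The denominator gap is real but secondary. Read naturally, the rule is sound. The gap could change the conclusion only when exactly 3 patients respond, 5 or more of the 20 are dropped, and the percentage is used in place of the count. The upward bias from dropping early losses is plausible in direction, but the documents give nothing from which to size it. The documents do not support a claim that the success rule is invalid or its error rate uncontrolled.

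**What to change.** 1. In Section 9.0, reprint the 95% interval for 4/20 as (0.07, 0.44) by the stated method, or as (0.06, 0.44) and name the exact method.
2. In Section 9.0, state that success is 4 or more responders among the 20 NSCLC patients who started SBRT and were not replaced under Section 5.8, and that patients without a post-SBRT response assessment count as non-responders. Use the same denominator for the exact binomial test. Report the response rate in assessable patients only as a sensitivity analysis.
3. Word the stopping count in Section 5.2.1 to match Section 9.0.

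Replacing the non-assessed patients would be another way to close the gap, but it would add patients and would still remove early losses from the rate. Counting them as non-responders avoids both.

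The cost is a few sentences and one corrected figure, with no extra patients. Against the natural count-of-4 reading, the chance of success does not change. Against a reading of at least 20% of assessable patients, with the worst-case 14 assessable, it would be 0.30 rather than 0.55 at an assumed true rate of 20%, and 0.64 rather than 0.84 at 30%.

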10.0 LABELING, PACKAGING, STORAGE AND RETURN OF CLINICAL SUPPLIES

10.1 Investigational Product

The investigator shall take responsibility for and shall take all steps to maintain appropriate records and ensure appropriate supply, storage, handling, distribution and usage of investigational product in accordance with the protocol and any applicable laws and regulations.

Clinical Supplies will be provided by Merck as summarized in Table 9.

Table 9. Product Descriptions

Product Name & Potency	Dosage Form
MK-3475 100 mg/ 4mL	Solution for Injection

10.2 Packaging and Labeling Information

Clinical supplies will be affixed with a clinical label in accordance with regulatory requirements.

10.3 Clinical Supplies Disclosure

This trial is open-label; therefore, the subject, the trial site personnel, the Sponsor and/or designee are not blinded to treatment. Drug identity (name, strength) is included in the label text; random code/disclosure envelopes or lists are not provided.

10.4 Storage and Handling Requirements

Clinical supplies must be stored in a secure, limited-access location under the storage conditions specified on the label.

Receipt and dispensing of trial medication must be recorded by an authorized person at the trial site.

Clinical supplies may not be used for any purpose other than that stated in the protocol.

10.5 Returns and Reconciliation

The investigator is responsible for keeping accurate records of the clinical supplies received from Merck or designee, the amount dispensed to and returned by the subjects and the amount remaining at the conclusion of the trial.

Upon completion or termination of the study, all unused and/or partially used investigational product will be destroyed at the site per institutional policy. It is the Investigator's responsibility to arrange for disposal of all empty containers, provided that procedures for proper disposal have been established according to applicable federal, state, local and institutional guidelines and procedures, and provided that appropriate records of disposal are kept.

11.0 LABORATORY CORRELATIVE/SPECIAL STUDIES

11.1 Handling of Tissue

Before initiation of systemic therapy, local surgical therapy may be performed to obtain fresh tumor tissue. After tissue is obtained, it will be subjected to flash freezing in liquid nitrogen

and SNAP frozen tissue will be stored for further studies. If a patient has a previously obtained paraffin-embedded tissue that is available, a portion may be used to conduct the studies mentioned below.

The SNAP frozen tissue specimens will be analyzed at Yale University. FFPE specimens will be analyzed for PD-L1.

11.2 Correlative Studies

Correlative studies will be conducted tissue specimens obtained before and during trial therapy. PD-L1 positivity will be determined on FFPE tissue. A number of additional biomarkers will be studied for their potential predictive value. These exploratory studies include (but are not limited to):

- 1) Markers to be studied on tumor cells: B7H1, PDL2, B7H4, Galactin-9.
- 2) Percent of tumor sample that constitutes CD4 and CD8 cells
- 3) Antigen-specific markers on T cells

Patients who undergo surgical procedures while on systemic treatment will also be asked to provide a research specimen to determine changes in the above markers in the context of response or resistance to therapy.

Immune monitoring will be performed as a part of this study. Peripheral blood lymphocytes (PBLs) and plasma will be collected before and during treatment, and when patients come off of study. Peripheral blood mononuclear cells will be separated and cryopreserved for T and B cell studies. Samples will be stored for future immunophenotyping studies and serological profiling, as well as cytokine profiling at the Yale Immune Monitoring Core Facility.

12.0 MEASUREMENT OF RESPONSE

Response will be evaluated by imaging studies as described in the study calendar. If symptoms develop or clinical deterioration occurs, patients may be imaged prior to the pre-specified time points for imaging.

Response of all systemic metastases will be evaluated in this study using two methods: the new international criteria proposed by the Response Evaluation Criteria in Solid Tumors (RECIST) Committee v1.1, and the Immune-Related Response Criteria (irRC). The irRC will be used to make protocol-related decisions regarding treatment response. Response by RECIST will be recorded for later analysis. RECIST version 1.1 stipulates that the number of lesions required to assess tumor burden for response determination has been reduced to a maximum of five total lesions (two lesions maximum per organ).

Briefly, measurable lesions must have a minimum size of 10 mm by CT scan (CT scan slice thickness no greater than 5 mm) in at least one dimension. Lesions with a longest diameter of <10 mm are considered non-measurable lesions and will be tracked as non-target disease. Tumor lesions in a previously irradiated area, or in an area subject to other loco-regional therapy, are not considered measurable unless there has been demonstrated progression in the lesion. Following SBRT, response will be measured in comparison to the most immediate pre-

SBRT imaging study, or imaging immediately following SBRT, whichever is most recent. For this purpose, the metastatic target chosen for SBRT will not qualify as a measurable lesion. For complete definitions of measurable and non-measurable disease, please refer to the RECIST v1.1 criteria.

12.1 Evaluation of Best Overall Response

The Best Overall Response is the best response recorded from the start of the treatment until disease progression/recurrence (taking as reference for progressive disease the smallest measurements recorded since the treatment started). For purpose of the primary endpoint of the study, the overall response will be measured during the post-SBRT MK-3475, in comparison to the most immediate pre-SBRT imaging.

12.2 Progression-Free and Overall Survival

For the purpose of the secondary endpoints of this study, PFS is defined as the time from initiation of study drug post-SBRT, until the first documented, confirmed progression of disease as described in Section 5. PFS will also be measured and report from the initiation of study drug, pre-SBRT. OS will be measure from the initiation of study therapy.

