3.2 Secondary Objectives

- (1) To determine the local control of SBRT, when SBRT is given with MK-3475
- (2) To determine the time to progression in patients receiving post-radiation MK-3475, in patients whose disease had previously progressed on MK-3475 or another anti-PD-1 therapy.
- (3) To determine the progression-free and overall survival in patients receiving MK-3475, who receive SBRT
- (4) To determine the safety and toxicity of the combination of SBRT and MK-3475
- (5) To examine potential predictive biomarkers in tumor samples and peripheral blood in patients treated with MK-3475 and SBRT.

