5.2.1 Study Design

This is a two-part study, including both phase 1b and 2a portions.

The **phase 1b** is an SBRT dose escalation study, in which patients with both NSCLC and melanoma will be enrolled. NSCLC patients will be enrolled and treated with MK-3475 until they have progression of disease (irPD). Patients who have progression within 12 months of study entry will be evaluated for SBRT and re-initiation of MK-3475. Patients who do not have progression of disease within that timeframe may continue to receive MK-3475 for up to 18 months per protocol. These patients will not be evaluable for the study endpoints, although their response rates and overall survival will be reported.

Melanoma and selected NSCLC patients will be enrolled after having progression of disease on prior PD-1 therapy (irPD). They will be immediately treated with SBRT, followed by re-initiation of MK-3475.

After progression of disease on an initial course of anti-PD-1 therapy (either prior to enrollment, or during trial therapy), a target for SBRT will be selected and patients will be assigned to one of two arms on the basis of the anatomic location of the target (Arm A: lung, Arm B: non-lung). The SBRT target will be chosen and ideally SBRT will be delivered as quickly as feasible after the last infusion of MK-3475. NSCLC patients who do not have a suitable SBRT target (as defined in section 5.2.3) on the imaging study that shows progression of disease may undergo interval re-imaging without further therapy, but if no suitable target has been identified for SBRT within 12 weeks of the last infusion of MK-3475, that patient will be removed from treatment and moved to survival follow up.

Patients may continue to receive MK-3475 post disease progression while radiation therapy with SBRT is scheduled. Patients who require continuing corticosteroid treatment, or who have adverse events (grade 3 or greater non-hematologic, or grade 2 pneumonitis) due to MK-3475 that do not resolve within 12 weeks of AE start date will not receive SBRT and will also be removed from study. Patients who develop grade 3 pneumonitis will be removed from the study, regardless of whether it resolves. SBRT will be delivered in dose cohorts as described below in section 5.3.

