6.0 STUDY CALENDAR – NSCLC PATIENTS WITHOUT PRIOR ANTI-PD-1 THERAPY

Trial Period:		Treatment												End of Treatment		Follow Up	
Treatment Cycle/Title:		Screening	1	2	3+	4+	At Progression ¹⁰	SBRT	1	2	3+	4+	At Progression, Discontinuation	Safety Follow-Up	Survival Follow-up		
Scheduling Window (Days):	-28 to -1	± 7	± 7	± 7	± 7	± 7	± 7		± 7	± 7	± 7	± 7	± 7	30 Days post End of Treatment (± 7)	Every 12 weeks (± 7)		
Informed Consent	X																
Medical History	X																
Full Physical Exam, VS & weight	X																
Height	X																
Medication Review	X	X	X	X	X	X	X		X	X	X	X	X				
CT chest/abdomen/pelvis ¹	X		X		X				X		X		X				
Directed Physical Exam, VS & weight		X	X	X	X	X	X		X	X	X	X	X				
ECOG Performance Status	X	X	X	X	X	X	X		X	X	X	X	X				
Adverse Event Assessment	X	X	X	X	X	X	X ³	X	X	X	X	X	X	X ¹⁴			
Pregnancy Test – Urine or Serum β-HCG	X ¹¹																
Archival or Fresh Tumor Collection ⁴	X ²																
CBC with Differential	X	X	X	X	X				X	X	X	X					
CMP, LDH	X	X	X	X	X				X	X	X	X					
TSH & Free T4 ¹⁵	X		X		X				X		X						
Selection of SBRT target ⁷						X											
Blood for correlative studies	X ^{5, 12}	X ^{5, 12}	X ⁵	X ⁵	X ⁵	X ⁵	X ⁵	X ^{5, 12}	X ^{5, 12}	X ⁵	X ⁵	X ⁵	X ⁵				
Survival follow-up															X		
Administer study drug, MK-3475 ⁹			X ¹¹	X	X	X ^{6, 13}			X ⁸	X	X	X ¹⁶					

¹ During week 3 every 2 cycles (during the last week of cycles 2 and 4), and then every 4 cycles (at the end of cycles 8, 12, etc.). See Section 8.5 for exceptions.

² Includes PD-L1 testing

³ Study visit the last day of SBRT

⁴ When feasible, if a biopsy is done for clinical purposes as per standard of care at any point during a subject's participation on trial, tissue may be collected at the time of the biopsy

⁵ Blood for correlative studies will be drawn at cycles 2 through 4 for both pre- and post-SBRT, then every even-numbered cycle thereafter (e.g. 6, 8, 10, etc.). If MK-3475 is held for any reason when blood for correlative samples is to be drawn, the blood may be drawn at the discretion of the Principal Investigator. When MK-3475 is resumed, blood for correlative samples will be taken as per the calendar above.

⁶ May be administered for up to 18 months if no disease progression. If no disease progression and > 12 months on study drug, patient cannot receive SBRT on trial

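### The main PFS clock in Section 12.2 starts at the post-SBRT restart of MK-3475 and so leaves out irradiated patients who never restart; the second clock has no stated event or population

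*Combined protocol and SAP*

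**What the plan says.** Section 12.2 sets two PFS clocks.

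- **Main clock.** "PFS is defined as the time from initiation of study drug post-SBRT", running "until the first documented, confirmed progression of disease as described in Section 5". Death is not named as an event.
- **Second clock.** "PFS will also be measured and report from the initiation of study drug, pre-SBRT". Neither event nor population is restated.

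Section 9.0 makes PFS the secondary endpoint, to be shown by Kaplan-Meier, with no analysis population or censoring rule. The matching objective in Section 3.2 is "To determine the progression-free and overall survival in patients receiving MK-3475, who receive SBRT".

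Section 5.2.1 expects every patient to go back on MK-3475 after SBRT, as soon as feasible, and gives no rule for those who do not. Section 5.2.3 makes the second course conditional when SBRT was stopped for toxicity: the event must resolve within 12 weeks. Section 9.0 expects losses among patients who progress and go on to SBRT: "we estimate that 30% will drop out, or otherwise be ineligible for assessment of response to post-SBRT MK-3475". The replacement rules in Section 5.8 cover patients with no SBRT fraction, or with SBRT left incomplete for reasons other than toxicity. They do not cover a patient who completes SBRT and never restarts drug.

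For NSCLC patients without prior anti-PD-1 therapy, Section 5.2.1 says "Patients who have progression within 12 months of study entry will be evaluated for SBRT and re-initiation of MK-3475", and a footnote to the Section 6.0 calendar adds "If no disease progression and > 12 months on study drug, patient cannot receive SBRT on trial". Melanoma and pretreated NSCLC patients go straight to SBRT.

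**The concern.** The main clock selects on something that happens after SBRT. Patients who decline, die, progress or have unresolved toxicity between SBRT and the first restart dose are likely to be those doing worst. A patient who never restarts cannot enter the Kaplan-Meier estimate at all, and a progression before restart has no valid time on this clock. Section 5.2.1 judges progression against imaging immediately before or after SBRT, so the reference scan can also predate the clock. A reader would probably take the result as PFS after SBRT, whereas it describes PFS in those who got as far as restarting.

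The second clock raises a different problem. In anti-PD-1-naive NSCLC patients, progression within about 12 months is the condition for receiving SBRT. Depending on the intended event and population, the curve may be fixed in advance or partly made of time in which no event was possible.

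PFS is the only secondary endpoint with an analysis stated in Section 9.0, and the NSCLC cohort is 20 patients without a control group. A few missing early failures would be visible in the curve.

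**Working it through.** The plan gives no PFS figure (no median, rate, event count or power), so there is nothing to reproduce. The checks below show what the definitions imply.

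**Main clock: patients left out**

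Let d be the share of irradiated patients who never restart and S(t) the PFS among restarters. If non-restarters count as failures from the start, PFS in all irradiated patients is (1 − d) × S(t).

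- d: not given in the documents. The 30% in Section 9.0 also covers other losses, for example patients who restart and leave before a scan, so it is a ceiling if that projection holds. Range used: 10%, 20%, 30%.
- S(6 months) = 30%: assumed.

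| d | Of 20 patients, on the curve | (1 − d) × 0.30 |
|---|---|---|
| 10% | 18 | 27% |
| 20% | 16 | 24% |
| 30% | 14 | 21% |

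At the ceiling, 6 of 20 are missing, and the restart-based figure exceeds the all-irradiated figure by a factor of 1/0.7 = 1.43.

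**Main clock: the gap works the other way**

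Starting at SBRT adds the SBRT-to-restart interval to each restarter's time. Assume a 1-month gap and exponential PFS after restart. The monthly hazard is −ln(0.30)/6 = 0.2007. Six months from SBRT is five months from restart, so restarters are at exp(−5 × 0.2007) = 36.7%. Multiplying by (1 − d) gives 33%, 29% and 26% for d = 10%, 20% and 30%. The two effects cancel at d = 1 − 0.300/0.367 = 18%. The direction of the net change is therefore not certain.

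**Second clock: three readings**

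Let T be the time from first pre-SBRT dose to first progression. The clock exists only for anti-PD-1-naive NSCLC patients, because the others have no pre-SBRT study drug.

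1. *Irradiated patients, event = first progression.* SBRT requires T ≤ about 12 months, so P(T > 12 | T ≤ 12) = 0 for any distribution of T. The limit runs from study entry, which is not defined; with screening up to 28 days before treatment, about 12 months from first dose is fair.
2. *Irradiated patients, event = post-SBRT progression.* Simulation with assumed pre-SBRT medians of 3 to 9 months, a 1.5-month gap and post-SBRT medians of 2 to 4 months gives 12-month PFS of about 16% to 46%. All time before SBRT is guaranteed event-free on this reading.
3. *Everyone who starts pre-SBRT drug, event = first progression.* For exponential medians of 3 to 9 months, 12-month PFS is 2^(−12/3) = 6% to 2^(−12/9) = 40%. It is 30% if the Section 9.0 projection of 30% still responding at 12 months is read as 30% progression-free. This is an ordinary first-course PFS.

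Section 12.2 does not choose among these. Section 5.2.1 calls patients without progression by 12 months not evaluable for the study endpoints and promises only their response rates and overall survival, so reading 3 is not clearly intended.

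**The case against.** The best defence is that the main clock answers the question the trial asks. The primary endpoint is response to post-SBRT MK-3475, and the time-to-progression objective in Section 3.2 concerns patients who receive post-radiation drug. A restart-based origin fits both, and the PFS curve is descriptive, with no test, target or decision attached. This stands as a reason to keep the restart-based curve. It does not settle the separate PFS objective, which names patients who receive SBRT, and it does not supply a rule for those who never restart.

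The size is also fairly disputed. Section 5.2.1 plans for all patients to restart, and Section 5.2.3 lets some patients with incomplete SBRT continue. A shift of 3 to 9 percentage points is small beside the precision available: 6 of 20 has an exact 95% interval of 12% to 54%. Early deaths are not lost to the trial, since OS runs from initiation of study therapy and survival follow-up continues off treatment.

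Moving time zero alone would not produce the 27% to 21% figures either. Section 12.2 names only confirmed progression as an event, scheduled imaging follows the MK-3475 cycles, and follow-up after stopping may be by telephone. Many non-restarters would be censored rather than failed. That objection is right, and the event definition has to change together with the origin.

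**Conclusion.** The concern holds in a limited form. As written, the main PFS is conditioned on restarting MK-3475, and irradiated patients who do not restart, or who progress first, are not properly counted. The illustrated effect of omission is a fall from 30% to between 27% and 21%. It rests on an assumed 6-month PFS, an assumed never-restart share of 10% to 30%, and non-restarters counted as failures; the SBRT-to-restart gap offsets some of it, and all of it when few fail to restart.

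The second clock needs a stated event and population. Under either reading confined to irradiated patients it says little about SBRT.

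Three stronger inferences are tempting and not supported:

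- That the second PFS is 0% at 12 months in everyone irradiated. This applies only to anti-PD-1-naive NSCLC patients, and only if the event is first progression and the set is the irradiated.
- That the plan expects 30% never to restart. Its figure covers any dropout or ineligibility for response assessment.
- That the reported PFS is certainly too high by a known amount. The documents give neither the never-restart rate nor the gap.

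The response-rate primary endpoint is not affected by the PFS clock.

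**What to change.** In Section 12.2:

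- Define post-SBRT PFS from the first SBRT fraction to progression or death from any cause, in every patient who received at least one fraction, whether or not MK-3475 was restarted.
- Keep the restart-based curve as a labelled sensitivity analysis, and report how many irradiated patients it leaves out.
- Report PFS from the first pre-SBRT MK-3475 dose to first progression or death in all anti-PD-1-naive NSCLC patients who start drug, including those never irradiated. Label it first-course PFS.

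The cost is mainly wording. The SBRT dates are already needed for the DLT window in Section 5.3, and deaths are collected in survival follow-up. The downside is that reported PFS may change and may be less favourable. Progression in non-restarters will be known only from whatever imaging is available, with survival follow-up supplying deaths, and the report should say so.
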